## Other Allowed Dose Interruptions for Pembrolizumab

See Section 6.6.4 for other allowed dose interruptions for pembrolizumab and lenvatinib/placebo and stop time and restart time of lenvatinib/placebo for minor/major procedures.

### 6.6.2 Dose Modification With Lenvatinib/Placebo

Lenvatinib/placebo dose reduction and interruption for participants who experience lenvatinib/placebo-pembrolizumab combination therapy-related toxicity will be in accordance with the dose modification guidelines described in [Table 5](#). An interruption of study intervention for more than 28 days will require Sponsor consultation and approval before treatment can be resumed. Participants who discontinue lenvatinib/placebo due to untoward toxicities can continue on the study receiving pembrolizumab as monotherapy.

The starting dose of lenvatinib/placebo is 20 mg/day. Dose reductions of lenvatinib/placebo occur in succession based on the previous dose level (14, 10, and 8 mg/day). Any dose reduction below 8 mg/day must be discussed with the Sponsor. Once the study intervention

dose has been reduced, it may not be increased at a later date, unless the dose has been mistakenly decreased; in this situation, Sponsor's approval is required to increase the dose.

Refer to the subsections below for management of hypertension (Section 6.6.2.1), proteinuria (Section 6.6.2.2), diarrhea (Section 6.6.2.3), hepatotoxicity (Section 6.6.2.4), thromboembolic events (Section 6.6.2.5), posterior reversible encephalopathy syndrome/reversible encephalopathy syndrome/reversible posterior leukoencephalopathy syndrome (Section 6.6.2.6), hypocalcemia (Section 6.6.2.7), hemorrhage (Section 6.6.2.8), gastrointestinal perforation or fistula formation (Section 6.6.2.9), QT prolongation (6.6.2.10), and osteonecrosis of the jaw (Section 6.6.2.11) as appropriate, before consulting the dose modification table ([Table 5](#)). For overlapping toxicities of pembrolizumab and lenvatinib/placebo, please refer to Section 6.6.3.

Table 5 Dose Modification Guidelines for Lenvatinib/Placebo-related Adverse Events

Treatment-related Toxicity a,b	Management	Dose Adjustment
Grade 1 or Tolerable Grade 2		
	Continue treatment	No change
Intolerable Grade 2c,d or Grade 3e,f		
First occurrence	Interrupt lenvatinib/placebo until resolved to Grade 0-1, or tolerable Grade 2	Reduce lenvatinib/placebo dose to 14 mg once a day (1-level reduction)
Second occurrence (same toxicity or new toxicity)	Interrupt lenvatinib/placebo until resolved to Grade 0-1, or tolerable Grade 2	Reduce lenvatinib/placebo dose to 10 mg once a day (1-level reduction)
Third occurrence (same toxicity or new toxicity)	Interrupt lenvatinib/placebo until resolved to Grade 0-1, or tolerable Grade 2	Reduce lenvatinib/placebo dose to 8 mg orally once a day (1-level reduction)
Fourth occurrence (same toxicity or new toxicity)	Interrupt lenvatinib/placebo	Discuss with Sponsor
Grade 4g: Discontinue Study Intervention		
Abbreviations: AE = adverse event; BMI = body mass index; CTCAE = Common Terminology Criteria for Adverse Events.		
Note: For grading see CTCAE version 4.0. Collect all AE grades (ie, decreasing and increasing CTCAE grade).		

 
a. An interruption of study intervention for more than 28 days will require Sponsor's approval before treatment can be resumed.
 
b. Initiate optimal medical management for nausea, vomiting, hypertension, hypothyroidism and/or diarrhea prior to any lenvatinib/placebo interruption or dose reduction.
 
c. Applicable only to Grade 2 toxicities judged by the participant and/or physician to be intolerable.
 
d. Obese participants (BMI <math>\geq 30</math>) with weight loss do not need to return to their baseline weight or within 10% of their baseline weight (ie, Grade 1 weight loss). These participants may restart study intervention at a lower dose once their weight remains stable for at least 1 week, and they have a minimum BMI of 25. The new stable weight should be used as the new baseline for further dose reductions.
 
e. For asymptomatic laboratory abnormalities, such as Grade <math>\geq 3</math> elevations of amylase and lipase that are not considered clinically relevant by the investigator, continuation of treatment should be discussed with Sponsor.
 
f. For Grade 3 thromboembolic event, permanently discontinue lenvatinib/placebo, see Section 6.6.2.5.
 
g. Excluding laboratory abnormalities judged to be nonlife-threatening, in which case manage as Grade 3.
 
		

### 6.6.2.1 Management of Hypertension

Hypertension is a recognized side effect of treatment with drugs inhibiting VEGF signaling. Investigators should therefore ensure that participants enrolled to receive treatment with lenvatinib/placebo have BP of  $\leq 150/90$  mm Hg at the time of study entry and, if known to be hypertensive, have been on a stable dose of antihypertensive therapy for at least 1 week before C1D1. Early detection and effective management of hypertension are important to minimize the need for lenvatinib/placebo dose interruptions and reductions.

Regular assessment of BP should be as detailed in the SoA (Section 1.3). Hypertension will be graded using NCI CTCAE v4.0, based on BP measurements only (and not on the number of antihypertensive medications).

If the participant's first BP measurement of the current assessment is elevated (ie, systolic BP  $\geq 140$  mm Hg or diastolic BP  $\geq 90$  mm Hg), the BP measurement should be repeated at least 5 minutes later. One BP assessment is defined as the mean value of 2 measurements at least 5 minutes apart. If the BP assessment (ie, the mean of the 2 BP measurements obtained at least 5 minutes apart) is elevated (systolic BP  $\geq 140$  mm Hg or diastolic BP  $\geq 90$  mm Hg), a confirmatory assessment should be obtained at least 30 minutes later by performing 2 measurements (at least 5 minutes apart) to yield a mean value.

Antihypertensive agents should be started as soon as elevated BP (systolic BP  $\geq 140$  mm Hg or diastolic BP  $\geq 90$  mm Hg) is confirmed on 2 assessments at least 30 minutes apart. The choice of antihypertensive treatment should be individualized to the participant's clinical circumstances and follow standard medical practice. For previously normotensive participants, appropriate antihypertensive therapy should be started when systolic BP  $\geq 140$  mm Hg or diastolic BP  $\geq 90$  mm Hg is first observed on 2 assessments at least 30 minutes apart. For those participants already on antihypertensive medication, treatment modification may be necessary if hypertension persists.

Lenvatinib/placebo should be withheld in any instance where a participant is at imminent risk to develop a hypertensive crisis or has significant risk factors for severe complications of uncontrolled hypertension (eg, BP  $\geq 160/100$  mm Hg, significant risk factors for cardiac disease, intracerebral hemorrhage, or other significant comorbidities). Once the participant has been on the same antihypertensive medications for at least 48 hours and the BP is controlled, lenvatinib/placebo should be resumed as described below.

Participants who have had systolic BP  $\geq 160$  mm Hg or diastolic BP  $\geq 100$  mm Hg must have their BP monitored on Day 15 (or more frequently as clinically indicated) until systolic BP has been  $\leq 150$  mm Hg and diastolic BP has been  $\leq 95$  mm Hg for 2 consecutive treatment cycles. If a repeat event of systolic BP  $\geq 160$  mm Hg or diastolic BP  $\geq 100$  mm Hg occurs, the participant must resume the Day 15 evaluation until systolic BP has been  $\leq 150$  mm Hg and diastolic BP has been  $\leq 95$  mm Hg for 2 consecutive treatment cycles.

The following guidelines should be followed for the management of systolic BP  $\geq 160$  mm Hg or diastolic BP  $\geq 100$  mm Hg confirmed on 2 BP assessments at least 30 minutes apart:

1. Continue study intervention and institute antihypertensive therapy for participants not already receiving antihypertensive therapy.
2. For those participants already on antihypertensive medication, the dose of the current agent may be increased, if appropriate, or 1 or more agents of a different class of antihypertensive should be added. Study intervention can be continued without dose modification.
3. If systolic BP  $\geq 160$  mm Hg or diastolic BP  $\geq 100$  mm Hg persists despite maximal antihypertensive therapy, then lenvatinib/placebo administration should be interrupted and restarted at 1 dose level reduction only when systolic BP  $\leq 150$  mm Hg and diastolic BP  $\leq 95$  mm Hg and the participant has been on a stable dose of antihypertensive medication for at least 48 hours.
  - If systolic BP  $\geq 160$  mm Hg or diastolic BP  $\geq 100$  mm Hg recurs on the first dose reduction despite optimal management of hypertension with antihypertensive medications (either by dose increase or the addition of a different class of antihypertensive), then lenvatinib/placebo administration should be interrupted and restarted at an additional dose reduction only when systolic BP  $\leq 150$  mm Hg and diastolic BP  $\leq 95$  mm Hg and the participant has been on a stable dose of antihypertensive medication for at least 48 hours.
  - If systolic BP  $\geq 160$  mm Hg or diastolic BP  $\geq 100$  mm Hg recurs on the second dose reduction despite optimal management of hypertension with antihypertensive medications (either by dose increase or the addition of a different class of antihypertensive), then lenvatinib/placebo administration should be interrupted and restarted at a third dose reduction only when systolic BP  $\leq 150$  mm Hg and diastolic BP  $\leq 95$  mm Hg and the participant has been on a stable dose of antihypertensive medication for at least 48 hours.
  - Additional dose reduction should be discussed with Sponsor.

The following guidelines should be followed for the management of Grade 4 hypertension (life-threatening consequences):

1. Institute appropriate medical management
2. Discontinue study intervention

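### Section 6.6.2.1 tells sites both to withhold and to continue lenvatinib/placebo for an untreated participant confirmed at or above both 160 and 100 mm Hg, and leaves open whether a restart after withholding carries a dose reduction

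*Combined protocol and SAP*

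**What the plan says.** Protocol Section 6.6.2.1 (Management of Hypertension) contains two sets of instructions.

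- **Withhold paragraph.** "Lenvatinib/placebo should be withheld in any instance where a participant is at imminent risk to develop a hypertensive crisis or has significant risk factors" (factors that make uncontrolled BP dangerous). Examples follow in parentheses, and BP ≥160/100 mm Hg is the first. Dosing is to restart as set out further down, "Once the participant has been on the same antihypertensive medications for at least 48 hours and the BP is controlled".
- **Numbered guidance**, for systolic ≥160 or diastolic ≥100 mm Hg confirmed on 2 assessments at least 30 minutes apart:
  - Item 1: "Continue study intervention and institute antihypertensive therapy for participants not already receiving antihypertensive therapy".
  - Item 2, for those already on such therapy: adjust or add agents. "Study intervention can be continued without dose modification".
  - Item 3: if the elevation "persists despite maximal antihypertensive therapy, then lenvatinib/placebo administration should be interrupted and restarted at 1 dose level reduction only when" systolic is ≤150 and diastolic ≤95 mm Hg on a stable antihypertensive dose for at least 48 hours. The sub-bullets repeat this with a second and a third reduction.

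Three other texts bear on the point.

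- The opening of 6.6.2.1: "Early detection and effective management of hypertension are important to minimize the need for lenvatinib/placebo dose interruptions and reductions".
- Table 5, footnote b: "Initiate optimal medical management for nausea, vomiting, hypertension, hypothyroidism and/or diarrhea prior to any lenvatinib/placebo interruption or dose reduction".
- Section 6.6.2 sends sites to the toxicity subsections "as appropriate, before consulting the dose modification table". It also bars any later increase of a reduced dose unless the decrease was a mistake, and then only with Sponsor approval.

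**The concern.** The same blood pressure serves as an example of when to withhold and falls within the range in which item 1 says to continue. A site with an untreated participant confirmed at, say, 165/105 mm Hg meets both instructions within one subsection, with no statement of precedence. Two sites acting in good faith could handle the same event in opposite ways.

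The restart adds a second divergence. The withhold paragraph gives no BP figure for control and relies on a forward reference. The text it leads to belongs to a different situation, elevation that persists or recurs despite therapy, and it includes a dose-level reduction. One site might restart at the same dose and another one level lower. Because a reduced dose may not be raised again except after a mistaken decrease, that difference stays with the participant.

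At stake are consistent management of a recognized toxicity and the summaries of interruption, reduction and exposure planned in Section 9.12.

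**Working it through.** The plan has no figure to reproduce. The check sets the instructions side by side.

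**Step 1: does item 1 cover lenvatinib/placebo?** Yes. Section 6 defines study intervention to include every investigational product and placebo. Item 3 is also the first item to interrupt lenvatinib/placebo, which presupposes that it was still being given.

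**Step 2: confirmed readings, case by case.**

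| Case | Withhold paragraph | Numbered guidance | Result |
|---|---|---|---|
| Systolic ≥160 and diastolic ≥100, no antihypertensive | Withhold | Item 1: continue | Direct conflict |
| Only one limit reached, no antihypertensive | Unclear whether the 160/100 example is met | Item 1: continue | Ambiguous |
| Both limits reached, already treated | Withhold | Item 2: may continue | Weaker; a site that withholds breaches neither |
| Persists despite maximal therapy | Withhold | Item 3: interrupt | No conflict on stopping |

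**Step 3: can timing reconcile the first case?** One might hold the drug until the reading is confirmed and then continue under item 1. That does not work. Confirmation takes at least 30 minutes, whereas the withhold paragraph allows resumption only after 48 hours on unchanged medication with BP controlled.

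**Step 4: does other text settle it?** Footnote b of Table 5 and the opening of 6.6.2.1 both lean toward treating before interrupting, which fits item 1. But Section 6.6.2 has sites read 6.6.2.1 before Table 5, so the footnote does not override the withhold paragraph. Where the protocol wants one rule to prevail it says so: the second liver criterion in Section 6.6.3 names the advice in Tables 3 and 5 and then overrides it. Section 6.6.2.1 has no such clause.

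**Step 5: restart.** The only restart text after the withhold paragraph is item 3 and its sub-bullets. It has three parts: BP ≤150 and ≤95 mm Hg; 48 hours on a stable antihypertensive dose; one dose-level reduction. The 48-hour part matches the withhold paragraph and the BP part can fill its missing figure. The reduction has no counterpart there, and item 3's entry condition need not be met by a participant withheld under that paragraph.

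**Step 6: difference per event.** Lenvatinib is taken once daily, so a withhold of at least 48 hours omits about 48/24 = 2 doses, against none under item 1. This assumes antihypertensive treatment starts when the drug is stopped. From the 20 mg starting dose, one level down is 14 mg, so restart readings differ by (20 − 14)/20 = 30% of the daily dose.

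**Step 7: who is affected now.** The note in Sections 6.1 and 6.6 stops lenvatinib/placebo for all participants, with exceptions on request for lenvatinib, and Section 6.1 ends the use of placebo. Section 6.6.2.1 also starts antihypertensives at confirmed systolic ≥140 or diastolic ≥90 mm Hg. To be untreated and confirmed at both higher limits, a participant must have passed the lower start point between assessments or missed the start of treatment.

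**The case against.** The best opposing case is that the withhold paragraph describes a judged clinical state, imminent crisis or major risk factors, and that the BP figure merely illustrates it. The numbered items would then be the general rule and the paragraph a high-risk exception. The surrounding text supports treating first, and both instructions use advisory wording. That reading would be sound if the exception had its own trigger. It does not: BP ≥160/100 mm Hg is a listed example of the exception and also lies inside the rule's range.

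Parts of the objection stand. The untreated case is uncommon by design, given the start point of 140 or 90 mm Hg. The forward reference does lead to a BP figure, so the open restart question is only the dose reduction. Continued lenvatinib already requires consulting the Sponsor, which gives sites a route for queries. Section 6 says its original text is kept for reference, but participants on lenvatinib by exception have no other hypertension dosing guidance in these documents.

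A reader might infer more than the text supports, in three ways.

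- **That all hypertension guidance is contradictory.** It is not. Item 2 is permissive and item 3 agrees on stopping.
- **That the liver text is a second dosing conflict.** The sentence under the first liver criterion in Sections 6.6.3 and 7.1 assumes reduced-dose lenvatinib/placebo after pembrolizumab was permanently stopped, a state that Section 6.6, Section 6.6.3 itself and Table 4 footnote a exclude. But every one of these texts ends with lenvatinib/placebo stopped. There is no competing order, so this is an editorial mismatch without shown consequence.
- **That past exposure data from the roughly 660 randomized participants are compromised.** The documents report neither how often such readings occurred nor how sites acted.

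**Conclusion.** The inconsistency is real and should be fixed, within narrow limits. The conflict is direct only when three conditions coincide: systolic ≥160 and diastolic ≥100 mm Hg, confirmation on 2 assessments, and no current antihypertensive therapy. The restart ambiguity is wider, since it can follow any withhold under that paragraph.

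The total size cannot be computed. The documents give neither the number of participants on lenvatinib by exception nor the frequency of such readings. What can differ is how individual participants are managed and, through that, the interruption and reduction summaries and possibly lenvatinib duration in Section 9.12, all descriptive. No effect is claimed on efficacy results, alpha or power.

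This rests on two assumptions. The first is that Section 6.6.2.1 still governs participants on lenvatinib by exception. The second is that the China provisions in Section 10.7.1 leave the instruction to stop lenvatinib/placebo in place: they lift only the sentence on leaving the study after the 30-day visit, although they also restore the original schema for China. If that second assumption is wrong, the reach is somewhat larger but the conflict is the same.

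**What to change.** Issue a clarification letter or amendment text that:

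1. reconciles the withhold paragraph of Section 6.6.2.1 with items 1 to 3 and with Table 5 footnote b, and says which prevails when both apply, including when only one BP limit is reached;
2. states what the forward reference on resumption covers: the BP and 48-hour conditions only, or the dose-level reduction as well.

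The sponsor's clinical team decides the rule; none is proposed here. The liver sentence in Sections 6.6.3 and 7.1 can be aligned editorially in the same document if convenient.

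The cost is drafting and distribution, with no new data or procedures. A letter is the lighter route. If the sponsor treats the change as an amendment, Appendix 1 requires regulatory submission and IRB/IEC approval, so it would sensibly be combined with any other pending change.

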### 6.6.2.2 Management of Proteinuria

Regular assessment of proteinuria should be conducted as detailed in the SoA (Section 1.3). Guidelines for assessment and management of proteinuria are as follows:

#### **Detection and Confirmation:**

- Perform urine dipstick testing per the SoA (Section 1.3). Urine dipstick testing is the preferred method for testing urinary protein, however, urinalysis may be used if the use of urine dipstick is not feasible.
- A 24-hour urine collection initiated as soon as possible and at least within 72 hours (or an immediate spot urine protein-to-creatinine ratio [UPCR] test) is required in the following situations:
  - The first (initial) occurrence of  $\geq 2+$  ( $\geq 100$  mg/dL) proteinuria on urine dipstick (or urinalysis) while the participants is receiving lenvatinib/placebo
  - A subsequent increase in severity of urine dipstick or urinalysis proteinuria occurring on the same lenvatinib/placebo dose level
  - When there has been a lenvatinib/placebo dose reduction and at the new dose level the urine protein dipstick result is  $\geq 2+$  ( $\geq 100$  mg/dL)
- A 24-hour urine collection (initiated as soon as possible and at least within 72 hours) to verify the grade of proteinuria is required when UPCR is  $\geq 2.4$ .

#### **Grading of Proteinuria:**

- Grading according to NCI CTCAE v4.0 will be based on the 24-hour urinary protein result if one has been obtained. Management of lenvatinib/placebo administration will be based on the grade of proteinuria according to [Table 5](#).

#### **Monitoring:**

- Urine dipstick or urinalysis testing for participants with proteinuria  $\geq 2+$  ( $\geq 100$  mg/dL) should be performed on D15 (or more frequently as clinically indicated) until the results have been 1+ (30 mg/dL) or negative for 2 consecutive treatment cycles.
- Proteinuria monitoring can be performed at the local laboratory or investigator site but must be managed by the site physician.
- In the event of nephrotic syndrome, lenvatinib/placebo must be discontinued.

### 6.6.2.3 Management of Diarrhea

An anti-diarrheal agent should be recommended to the participant at the start of study intervention and participants should be instructed and educated to initiate anti-diarrheal treatment at the first onset of soft bowel movements. The choice of anti-diarrheal agent

should be individualized to the participant's clinical circumstances and follow standard medical practice. If signs/symptoms of diarrhea persist despite optimal medical management, instructions contained in [Table 5](#) should be followed.

#### **6.6.2.4 Management of Hepatotoxicity**

Liver function tests (alanine transaminase [ALT], aspartate transaminase [AST], bilirubin levels) should be conducted as detailed in the SoA (Section 1.3) and as clinically indicated. If signs/symptoms indicating liver injury occur, instructions contained in [Table 5](#) should be followed. Appropriate supportive care should be provided together with close monitoring. If hepatic failure (any grade per CTCAE v4.0) occurs, lenvatinib/placebo must be discontinued.

#### **6.6.2.5 Management of Thromboembolic Events**

Participants should be advised to pay attention to symptoms suggestive of venous thromboembolic events, which include acute onset of shortness of breath, dyspnea, chest pain, cough, hemoptysis, tachypnea, tachycardia, cyanosis, and DVT signs including lower-extremity swelling and warmth to touch or tenderness. In case any of these symptoms appear, participants should be instructed to report such symptoms promptly to the treating physician. If a thromboembolic event is confirmed, instructions contained in [Table 5](#) should be followed. Appropriate supportive care should be provided together with close monitoring. If a participant experiences a Grade 3 or life-threatening (Grade 4) thromboembolic reactions, including pulmonary embolism, lenvatinib/placebo must be discontinued.

Arterial thromboembolic events (eg, new onset, worsening, or unstable angina, myocardial infarction, transient ischemic attack, and cerebrovascular accident) of any grade require study intervention discontinuation.

